2.3.2 Secondary Endpoints

Not applicable.

2.3.3 Exploratory Endpoints

Not applicable.

3 STUDY POPULATION

3.1 Selection of Study Population

The study population will include approximately 400 men with metastatic castration-resistant prostate cancer known to have risk factor(s) for seizure.

In order to avoid patient enrollment being dominated by single patient characteristics in the study, the number of subjects enrolled under each risk factor will be monitored closely. Subjects enrolled under a specific risk category i.e., class of medication may be limited.

3.2 Inclusion Criteria

Subject is eligible for the study if all of the following apply:

1. Institutional Review Board (IRB)-/Independent Ethics Committee (IEC)-approved written Informed Consent and privacy language as per national regulations (e.g., Health Insurance Portability Accountability Act (HIPAA) authorization for United States sites) must be obtained from the subject or legally authorized representative prior to any study-related procedures (including withdrawal of prohibited medication, if applicable).
2. Subject has histologically confirmed metastatic adenocarcinoma of the prostate.
3. Subject has ongoing androgen deprivation therapy with a GnRH analogue (agonist or antagonist) or bilateral orchiectomy (i.e., surgical or medical castration).
4. Subject has disease progression by at least 1 of the following:
 - a) PSA progression defined by a minimum of 2 rising PSA levels with an interval of at least 1 week between each draw;
 - b) Bone disease progression as defined by Prostate Cancer Working Group 2 guidelines (at least 2 new lesions) on bone scan; or
 - c) Soft tissue disease progression as defined by RECIST 1.1
5. For subjects who have not had an orchiectomy, there must be a plan to maintain effective GnRH-analogue therapy for the duration of the study.
6. Subject must have failed at least one course of androgen deprivation therapy (ADT), i.e., treatment with GnRH analogues.
7. Subject has an ECOG performance status of 0-2.
8. Subject has been evaluated by a local neurologist prior to study entry who has determined the subject has at least one risk factor for seizure including:

- a) past history of seizure due to any cause except a single febrile seizure in childhood. Patients with a history of seizures should not have had a seizure within 12 months of Screening and must have had no anticonvulsants for 12 months prior to Screening.
 - b) history of cerebrovascular accident (CVA) or transient ischemic attack (TIA),
 - c) history of traumatic brain or head injury with loss of consciousness,
 - d) unexplained loss of consciousness within the last 12 months,
 - e) presence of a space occupying lesion in the brain including previously treated brain metastasis(es) or primary CNS tumor,
 - f) history of arteriovenous malformations of the brain,
 - g) history of brain infection (i.e., abscess, meningitis, or encephalitis),
 - h) current use of medication that may lower seizure threshold (see Appendix [12.1](#)),
 - i) presence of Alzheimer's disease, meningioma, leptomenigeal disease from prostate cancer.
9. Male subject and his female partner who is of childbearing potential must use two acceptable methods of birth control (one of which must include a condom as a barrier method of contraception) starting at Screening and continuing throughout the study period and for 3 months after final study drug administration.
- a) Two acceptable forms of birth control include:
 - i. Condom (barrier method of contraception), AND
 - ii. One of the following acceptable forms of contraception is required:
 1. Established use of oral, injected or implanted hormonal methods of contraception.
 2. Placement of an intrauterine device (IUD) or intrauterine system (IUS).
 3. Barrier methods of contraception: Occlusive cap (diaphragm or cervical/vault caps) with spermicidal foam/gel/film/cream/suppository).
 4. Vasectomy or surgical castration at least 6 months prior to Screening.
10. Male subject must use a condom, if having sex with a pregnant woman.
11. Male subject must not donate sperm starting at Screening and throughout the study period and for at least 3 months after final drug administration.
12. Subject is able to swallow the study drug and comply with study requirements.
13. Subject agrees not to participate in another interventional study while on treatment.

Waivers to the inclusion criteria will **NOT** be allowed.

3.3 Exclusion Criteria

Subject will be excluded from participation if any of the following apply:

1. Subject with a history of exposure to enzalutamide.
2. Subject has severe concurrent disease, infection, or co-morbidity that, in the judgment of the Investigator, would make the subject inappropriate for enrollment.
3. Subject is currently treated with anti-epileptics.

4. Subject has a history of seizure in the past 12 months of Screening as assessed by neurology examination and history.
5. Subject with rapidly progressive visceral disease who has not received and is thought able to tolerate cytotoxic chemotherapy. (However, subject who has previously received cytotoxic chemotherapy is permitted).
6. Subject has clinical signs suggestive of high or imminent risks for pathological fracture, spinal cord compression and/or cauda equina syndrome.
7. Subject's absolute neutrophil count is $< 1500 /\mu\text{L}$, platelet count is $< 100,000/\mu\text{L}$, or hemoglobin is $< 5.6 \text{ mmol/L}$ (9 g/dL) at Screening.
8. Subject's total bilirubin is $\geq 1.5 \times \text{ULN}$ (except for subjects with documented Gilbert's disease) or alanine aminotransferase (ALT) or aspartate aminotransferase (AST) is $\geq 2.5 \times \text{ULN}$ at Screening.
9. Subject's estimated creatinine clearance (C_{cr}) is less than 30 mL/min by the Cockcroft and Gault formula (Creatinine Clearance (mL/min) = $(140 - \text{age})(\text{wt kg}) / 72 \times \text{serum creatinine (mg/100 ml)}$) [Cockcroft, 1976] at Screening.
10. Subject has uncontrolled hypertension as indicated by a resting systolic blood pressure $> 160 \text{ mmHg}$ or diastolic blood pressure $> 100 \text{ mmHg}$ at Screening.
11. Subject has received an investigational agent within 4 weeks or 5 half lives whichever is longer prior to Day 1.
12. Subject has shown a hypersensitivity reaction to the active pharmaceutical ingredient or any of the capsule components, including Labrasol, butylated hydroxyanisole, and butylated hydroxytoluene.
13. Subject has any condition which, in the Investigator's opinion, makes the subject unsuitable for study participation.

Waivers to the exclusion criteria will **NOT** be allowed.

4 TREATMENT(S)

4.1 Identification of Investigational Product

4.1.1 Enzalutamide

Enzalutamide has the chemical name 4-{3-[4-Cyano-3-(trifluoromethyl)phenyl]-5,5-dimethyl-4-oxo-2-sulfanylideneimidazolidin-1-yl}-2-fluoro-*N*-methylbenzamide. It is a white to off-white solid that is insoluble in water and no salt forms are available at ~pH 2 to 10.

Enzalutamide capsules are white to off-white oblong capsules. The soft gelatin capsules are filled with a clear, yellowish solution which contains the two antioxidants, butylated hydroxyanisole, and butylated hydroxytoluene, and enzalutamide active ingredient (40 mg), all dissolved in the non-ionic surfactant, Labrasol® (Caprylocaproyl Polyoxylglycerides).

Enzalutamide should be stored in a secure location with limited access at 77°F (25°C), with excursions permitted to 59°F to 86°F (15°C to 30°C). Subjects will be instructed to store study drug at room temperature out of the reach of children.

4.1.2 Comparative Drug(s)

This section is not applicable as this is a single-arm study.

4.1.3 Seizure Therapy

Standard anticonvulsant measures, if indicated in the event of a seizure (NOTE: concomitant medication restrictions).

If the decision is made to continue a subject in the study after a first seizure, treatment including anti-seizure medication may be administered as recommended by the local neurologist and guided by the following restrictions.

- Enzalutamide has the potential to interact with some anti-seizure drugs.
- Acceptable drugs unlikely to cause interactions are
 - Levetiracetam
 - Gabapentin
 - Pregabalin
- Drugs which are acceptable but should be **administered with caution** include
 - Ethosuccimide
 - Lacosamide
 - Lamotrigine
 - Oxcarbazepine
 - Topiramate
 - Valproate
 - Zonisamide
- Benzodiazepines **should not be used** for maintenance therapy of seizure
- Other anti-seizure medications **not permitted in the study** include
 - Carbamazepine
 - Phenytoin
 - Phenobarbital
 - Primidone
 - Felbamate
 - Vigabatrin
 - Retigabine

4.2 Suspected Seizure Event Management

Each subject will be given a patient card with the following information; a list of signs and symptoms of a suspected seizure (Seizure Description Subject Information) and a Suspected Seizure Event Questionnaire list as well as instructions regarding what to do in the event of a suspected seizure for awareness.

The subject will contact the Investigator immediately (within 24 hours) after onset of a suspected seizure event and return to the site with best efforts in 3 days after event for evaluation by the local neurologist.

Investigator will:

- Instruct the subject to stop taking the enzalutamide study drug until after the clinical assessment has been completed by the neurologist. (Note: this could be a temporary stoppage, if the event turns out not to have been deemed a seizure, or is a 1st seizure with good benefit/risk ratio for continuing study drug.)
- Instruct the subject to complete the Suspected Seizure Event Questionnaire with input from any witness(es) to suspected events.
- Schedule a clinic visit to be evaluated by the local neurologist.

Evaluation by a local neurologist is required including electroencephalogram (EEG) and magnetic resonance imaging (MRI) procedures as soon as possible after a potential seizure event occurrence. A description of the events leading up to the seizure will be obtained from the individual and any witnesses.

The study site will interview the subject and any witnesses, if possible, regarding the event. The study site will complete a Suspected Seizure Event Questionnaire including a Cover Sheet which will be signed by the PI/Sub-Investigator and included as part of the package to the IAC. The site will review the Suspected Seizure Event Questionnaire completed by the subject, if available. The subject Suspected Seizure Event Questionnaire is a tool to capture information of the suspected event which the PI/Sub-Investigator will utilize for completion of their evaluation when available. The Questionnaire completed by the subject will not be collected.

Subjects will be treated as indicated by the local neurologist including acceptable anti-convulsants. Anticonvulsant substrates of CYP3A4, CYP2C9 or CYP2C19 with a narrow therapeutic index are **not** permitted (e.g., anticonvulsant medications including carbamazepine, phenytoin, phenobarbital, primidone, felbamate, vigabatrin, and retigabine).

Subjects may continue on enzalutamide at the discretion of Investigator while the evaluation for a first possible seizure is ongoing. The dose of enzalutamide may be continued while the subject is on treatment with anticonvulsant therapy. If a subject experiences a second confirmed seizure by IAC, the subject will be discontinued from the study.

All relevant information, including the completed seizure assessment questionnaire, the local neurologist's evaluation, and results of the MRI of the brain and EEG, will be submitted to the IAC for evaluation. Results of the assessment of the IAC will be provided to the Investigator and the subject will be allowed to continue in the study if the event is determined to be a first confirmed seizure. If the seizure is determined by the IAC to be a second confirmed seizure event in the study, the subject will be withdrawn from the study. If it is determined that the event did not meet criteria for a confirmed seizure, the subject can continue in the study if no other discontinuation criteria have been met.

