If the treating neurologist deems the event not to have been a seizure, enzalutamide may be restarted. If the neurologist determines that a seizure has occurred and the event is a first seizure, prior to the IAC assessment, an allowable anticonvulsant may be administered on a maintenance basis and enzalutamide may be restarted if desired by the investigator and subject, AFTER confirmation of clinical benefit as assessed by the Investigator. Results of the assessment of the IAC will be provided to the investigator and the subject will be allowed to continue in the study if the event is determined to be a first confirmed seizure.

In the event of a second seizure, enzalutamide will be held until the IAC's review is completed. Upon IAC confirmation of a second seizure, enzalutamide may not be restarted and the subject will be discontinued from the study.

All relevant information, including the completed seizure assessment questionnaire, the neurologist's evaluation, and results of the MRI of the brain and EEG, will be submitted to the IAC for evaluation. Results of the assessment of the IAC will be provided to the investigator and the subject will be allowed to continue in the study if the event is determined to be a first confirmed seizure. If the seizure is determined by the IAC to be a second confirmed seizure event in the study,

the subject will be withdrawn from the study. If it is determined that the event did not meet criteria for a confirmed seizure, the subject can continue in the study if no other discontinuation criteria have been met.

DSMB and IAC

A DSMB will be established for this study and remain active for the study duration. The DSMB will examine safety data and be informed of seizure events as expediently as possible. The role and responsibilities of the DSMB will be described in the DSMB charter which will be in place for the start of the study. Details of statistical boundaries for monitoring of the seizure event will be provided in the DSMB charter.

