The subject will contact the Investigator immediately (within 24 hours) after onset of a suspected seizure event and return to the site with best efforts in 3 days after event for evaluation by the local neurologist.

Investigator will:

- Instruct the subject to stop taking the enzalutamide study drug until after the clinical assessment has been completed by the neurologist. (Note: this could be a temporary stoppage, if the event turns out not to have been deemed a seizure, or is a 1st seizure with good benefit/risk ratio for continuing study drug.)
- Instruct the subject to complete the Suspected Seizure Event Questionnaire with input from any witness(es) to suspected events.
- Schedule a clinic visit to be evaluated by the local neurologist.

Evaluation by a local neurologist is required including electroencephalogram (EEG) and magnetic resonance imaging (MRI of the brain) procedures as soon as possible after a potential seizure event occurrence. A description of the events leading up to the seizure will be obtained from the individual and any witnesses.

The study site will interview the subject and any witnesses, if possible, regarding the event. The study site will complete a Suspected Seizure Event Questionnaire including a Cover Sheet which will be signed by the PI/Sub investigator and included as part of the package to the IAC. The site will review the Suspected Seizure Event Questionnaire completed by the subject, if available. The subject Suspected Seizure Event Questionnaire is a tool to capture information of the suspected event which the PI/Sub-investigator will utilize for completion of their evaluation when available. The Questionnaire completed by the subject will not be collected.

Subjects will be treated as indicated by the local neurologist including acceptable anti-convulsants, if indicated.

If the treating neurologist deems the event not to have been a seizure, enzalutamide may be restarted.

If the neurologist determines that a seizure has occurred and the event is a first seizure prior to the IAC assessment, an allowable anticonvulsant may be administered on a maintenance basis and enzalutamide may be restarted if desired by the investigator and subject, AFTER confirmation of clinical benefit as assessed by the Investigator. Results of the assessment of the IAC will be provided to the investigator and the subject will be allowed to continue in the study if the event is determined to be a first confirmed seizure.

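### Protocol Section 4.2 allows enzalutamide to continue while a first possible seizure is evaluated, without limiting this to the period after the neurologist's assessment

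*Protocol*

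**What the plan says.** Protocol Section 4.2 is where a site looks for how to manage a suspected seizure. The subject reports the event within 24 hours and is asked to "return to the site with best efforts in 3 days after event for evaluation by the local neurologist". Among the things the Investigator will do is this: "Instruct the subject to stop taking the enzalutamide study drug until after the clinical assessment has been completed by the neurologist". A note adds that the stop may prove temporary, if the event is judged not to have been a seizure or "is a 1st seizure with good benefit/risk ratio for continuing study drug".

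After the paragraphs on the neurologist's work-up and on anticonvulsant treatment, the same section says: "Subjects may continue on enzalutamide at the discretion of Investigator while the evaluation for a first possible seizure is ongoing". It then says that the questionnaire, the neurologist's findings, the MRI and the EEG "will be submitted to the IAC for evaluation".

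The Synopsis (Suspected Seizure Event Management) and Section 2.2.1 carry the same stop instruction, followed by an explicit restart rule. For an event that was not a seizure: "If the treating neurologist deems the event not to have been a seizure, enzalutamide may be restarted". For a first seizure, before the IAC has ruled: "enzalutamide may be restarted if desired by the investigator and subject, AFTER confirmation of clinical benefit as assessed by the Investigator". Neither place contains the permission to continue during evaluation.

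**The concern.** Section 4.2 gives a mandatory hold and then a discretionary permission, and does not say how they fit together. A site acting on the hold would stop the drug at once. A site acting on the permission, taken at its word, could keep dosing before any neurologist has seen the subject.

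The subjects were selected for seizure risk and seizure is the known toxicity under study. Section 1.3 says that safety in patients with predisposing factors is not known, and that there is no trial experience of giving enzalutamide again after a seizure. About 135 centers are planned, so the rule should not depend on which sentence a site reads. A wrong dose is also a notifiable deviation under Section 8.1.6, and compliance cannot be judged consistently against two rules.

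**Working it through.** The point rests on wording. Setting the three accounts side by side:

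| Step | Synopsis and Section 2.2.1 | Section 4.2 |
|---|---|---|
| Suspected event reported | Stop drug until the neurologist's clinical assessment is complete | Same |
| Event judged not a seizure | Restart allowed | No separate rule; the note says the stop may be temporary |
| First seizure, IAC decision pending | Restart allowed once the Investigator confirms clinical benefit | No such condition; the note mentions a good benefit/risk ratio |
| Evaluation of a first possible seizure ongoing | No permission to continue | May continue at Investigator discretion |

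**Does the wording fix the stage?** Outside the disputed sentence, Section 4.2 uses the noun 'evaluation' five times: three for the neurologist, one for the principal or sub-investigator, one for the IAC. Section 5.4.6 and Table 1 use it for the neurologist's step. The word can therefore refer to either stage. Section 2.2.1 is explicit where Section 4.2 is not: its restart rule applies once the neurologist has determined that a seizure occurred and "the event is a first seizure prior to the IAC assessment".

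**Is the benefit condition covered elsewhere?** In part. Besides the note in Section 4.2, the Synopsis (Study Design Overview) calls for disease assessment after a seizure, and Table 1 schedules one at the Suspected Seizure Visit. The Flow Chart note, Table 1 footnote h and the last paragraph of Section 2.2.1 tie the assessment to a confirmed first seizure, so they do not clearly govern the period before the IAC decision.

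**Size per event.** Assumptions: the neurologist visit is on day 3 (the best-efforts target), the clinical assessment is completed then, and the subject reports 0 to 24 hours after onset.

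- Reported at once: 3 doses × 160 mg = 480 mg.
- Reported at 24 hours: 2 doses × 160 mg = 320 mg.

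For context, Section 1.2.2.1 gives a terminal half-life of about 5.8 days. With simple first-order decay, a hold of t days lowers parent-drug concentration by 1 − 2^(−t/5.8): about 21% for 2 days and 30% for 3 days.

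**Number of events.** The affected quantity is suspected events, and the documents give no figure for them. The planning rate concerns seizures only: 2.8 per 100 patient-years × 4/12 = 0.93% (as in Section 7.1), which is 0.0093 × 350 ≈ 3.3 or 0.0093 × 400 ≈ 3.7 subjects in 4 months. Suspected events that are not confirmed, and events in the extension, come on top.

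**Effect on the analysis.** A subject with a confirmed first seizure in the 4-month period is evaluable and counted whatever happens to dosing afterwards. Incidence per patient-time uses only the first event (SAP 7.5.1.2).

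**The case against.** The strongest reply is that the two instructions can be reconciled:

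- **Position.** The disputed sentence comes after the neurologist steps and before submission to the IAC. In the Synopsis and Section 2.2.1 that slot holds the rule allowing restart before the IAC assessment. The sentence that follows, on dosing alongside anticonvulsants, matches the rest of that rule.
- **Terms.** The hold ends with the clinical assessment. Evaluation can be read more broadly, to include the EEG, the MRI and the IAC step, and so can still be under way after the hold has ended. A first event also remains only possible until the IAC rules.
- **Usage.** The protocol uses 'continue' for dosing after a stop, including in the note in Section 4.2. The choice of 'continue' over 'restart' therefore proves little.
- **Weight.** The stop instruction is mandatory and stated three times. The benefit condition is explicit in two other places, and a few days' hold lowers drug levels only partly.

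Most of this stands. It makes the IAC-interval reading the probable intention, and it rules out calling Section 4.2 flatly self-contradictory, which a reader might infer from the two sentences alone. It does not remove the problem: nothing in Section 4.2 limits the permission to that interval. Even on the reconciled reading, the sentence leaves dosing to Investigator discretion without repeating the requirement to confirm clinical benefit.

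**Conclusion.** The permission in Section 4.2 is wrong as written. Taken literally, it allows dosing during a period in which the same section, the Synopsis and Section 2.2.1 require a hold. The probable intention is consistent with the hold, but it is not stated.

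The consequence is for subject safety and uniform conduct. It amounts to about 2 to 3 daily doses per suspected event under the day-3 assumption, and more if the visit is later. The total cannot be sized, because the number of suspected events is not given.

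A reader might go further and infer that sites have dosed through unassessed seizures, or that the seizure estimate is compromised. The documents support neither. They show nothing about how sites read the text, and the primary endpoint is unaffected because a first confirmed seizure counts under both readings.

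**What to change.** Replace the disputed sentence in Section 4.2 with the rule already in the Synopsis and Section 2.2.1, for example:

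*Enzalutamide is held until the neurologist's clinical assessment is complete. If the event is deemed not a seizure, enzalutamide may be restarted. If it is deemed a first seizure, enzalutamide may be restarted before the IAC assessment, if desired by the Investigator and subject, only after the Investigator confirms clinical benefit.*

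The cost is a clarification amendment and a letter to sites. Sample size, endpoint and analysis do not change.

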In the randomized clinical trial CRPC2, 7 of 800 (0.9%) patients treated with enzalutamide 160 mg once daily experienced a seizure. No seizures occurred in patients treated with placebo. The onset of seizure events ranged from 31 to 603 days after initiation of enzalutamide. Patients experiencing seizure were permanently discontinued from enzalutamide therapy and all seizures resolved. There is no clinical trial experience re-administering enzalutamide to patients who experienced seizures. The safety of enzalutamide in patients with predisposing factors for seizure is not known because these patients were excluded from the trial. These exclusion criteria included a history of seizure, underlying brain injury with loss of consciousness, transient ischemic attack within the previous 12 months, cerebral vascular accident, brain metastases, brain arteriovenous malformation or the use of concomitant medication that may lower the seizure threshold.

As of the cutoff date of 01Jan 2014, seizure occurred in <1% of prostate cancer patients receiving enzalutamide who previously received docetaxel (chemotherapy), and < 0.1% of prostate cancer patients receiving enzalutamide who had not received chemotherapy.

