In the event of a second seizure, enzalutamide will be held until the IAC's review is completed. Upon IAC confirmation of a second seizure, enzalutamide may not be restarted and the subject will be discontinued from the study.

All relevant information, including the completed seizure assessment questionnaire, the local neurologist's evaluation, and results of the MRI of the brain and EEG, will be submitted to the IAC for evaluation. Results of the assessment of the IAC will be provided to the Investigator and the subject will be allowed to continue in the study if the event is determined to be a first confirmed seizure. If the seizure is determined by the IAC to be a second confirmed seizure event, the subject will be withdrawn from the study. If it is determined that the event did not meet criteria for a confirmed seizure, the subject can continue in the study if no other discontinuation criteria have been met.

Disease assessments should be performed regularly per standard of care or when there is clear clinical evidence of progression, while the subjects are receiving enzalutamide and also upon confirmation of a first seizure to confirm clinical risk/benefit profile to continue enzalutamide.

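### Protocol Section 4.2 stops enzalutamide for a suspected seizure, then allows a man with a first possible seizure to continue during an evaluation it does not identify

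*Protocol*

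**What the plan says.** Protocol Section 4.2 lists what the investigator does after a suspected seizure, including: "Instruct the subject to stop taking the enzalutamide study drug until after the clinical assessment has been completed by the neurologist". A note adds that the stop may prove temporary, if the event is judged not to be a seizure or "is a 1st seizure with good benefit/risk ratio for continuing study drug". The section then requires evaluation by a local neurologist with EEG and MRI, and treatment as the neurologist directs. After that come two permissive sentences: "Subjects may continue on enzalutamide at the discretion of Investigator while the evaluation for a first possible seizure is ongoing", and "The dose of enzalutamide may be continued while the subject is on treatment with anticonvulsant therapy". The next paragraph sends the case file to the IAC.

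The Synopsis (Suspected Seizure Event Management) and Section 2.2.1 give the same stop instruction but continue differently:

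- Not a seizure: "If the treating neurologist deems the event not to have been a seizure, enzalutamide may be restarted".
- A first seizure in the neurologist's judgment, with the IAC still to rule: an allowable anticonvulsant may be given and "enzalutamide may be restarted if desired by the investigator and subject, AFTER confirmation of clinical benefit as assessed by the Investigator".
- A second seizure: "In the event of a second seizure, enzalutamide will be held until" the IAC has finished its review.

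Disease assessments after a seizure are called for in the Synopsis (Study Design Overview), the flow-chart note, Table 1 with footnote h, and Section 2.2.1.

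**The concern.** Section 4.2 is the section a site would open when a suspected seizure is reported. Two sites could treat the same event differently and each point to Section 4.2: one holds the drug, the other keeps dosing on the investigator's discretion. A monitor could not readily say whether the second site had committed an incorrect-dose deviation under Section 8.1.6.

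The stake is patient safety. These men have risk factors that earlier trials excluded, and Section 1.3 says: "There is no clinical trial experience re-administering enzalutamide to patients who experienced seizures". The general safeguards do not settle the matter. Reporting of potential seizures as SAEs within 24 hours (Sections 5.5.2 and 5.5.5), notice to the DSMB (Section 1.4) and removal for undue risk (Section 6.1) all remain in force, but none of them holds the drug before the neurologist has assessed the man. Suspected-seizure visits also occur in the extension period (Table 1, footnote c), so the ambiguity lasts beyond the four-month period.

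**Working it through.** The main check is a comparison of text, stage by stage.

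| Stage | Synopsis and Section 2.2.1 | Section 4.2 |
|---|---|---|
| Suspected event, neurologist not finished | Drug stopped | Drug stopped, but continuation at discretion if *evaluation* means the work-up |
| Neurologist: not a seizure | May restart | Covered only by the note on temporary stoppage |
| Neurologist: first seizure, IAC pending | May restart if investigator and subject wish it, after benefit is confirmed | Note on benefit/risk; continuation at discretion if *evaluation* means the IAC review; dosing alongside an anticonvulsant allowed without a stated condition |
| Second seizure, IAC pending | Drug held | Hold not restated |
| Second seizure confirmed by the IAC | Discontinued | Discontinued |

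**Reading 1: the evaluation is the neurologist's work-up.** Section 4.2 uses the word this way when it requires EEG and MRI. The sentence then allows dosing in exactly the interval for which the same section orders a stop. This is a direct contradiction.

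**Reading 2: the evaluation is the IAC review.** Section 4.2 also uses the word this way, in the following paragraph. The stop instruction is then intact. But discretion alone stands where the Synopsis and Section 2.2.1 require the wish of both parties and prior confirmation of benefit. Within Section 4.2 that condition survives only as the note's reference to benefit/risk.

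A discrepancy remains on either reading, though a different one.

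**Number of men who could meet the ambiguity.** Inputs: 2.8 seizures per 100 patient-years and 350 evaluable subjects (Section 7.1); about 400 men (Section 3.1).

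- The protocol's own figure: 2.8/100 × 4/12 = 0.0093, which reproduces the 0.93% in Section 7.1.
- First seizures in four months, everyone contributing full time: 400 × 2.8/100 × 4/12 = 3.73.
- If the roughly 50 expected drop-outs contributed no time: 350 × 2.8/100 × 4/12 = 3.27.
- If the rate were double, an assumption made because the earlier studies excluded these risk factors (Section 2.2.1): 400 × 5.6/100 × 4/12 = 7.47.

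Events in the extension period, and suspected events later judged not to be seizures, are additional. The documents give no figure for the latter.

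**The case against.** The best defense is that the IAC reading is the natural one. The sentence follows the stop, the work-up and neurologist-directed treatment. It stands where the other two sections allow restart before the IAC rules, and a seizure the IAC has not yet confirmed is reasonably called possible. Nor does it help to stress that the sentence says *continue* and not *restart*, because the protocol uses *continue* elsewhere for resuming after a stop. All of this is fair and makes the second reading plausible. It does not remove the ambiguity, and on that reading the restart condition is still missing.

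A second defense is that a benefit check exists elsewhere. That is true: Table 1 marks a disease assessment at the suspected-seizure visit, and the flow-chart note ties one to continuing on an anticonvulsant. So a reader who infers that the protocol as a whole has dropped the benefit check goes too far. What stands is that Section 4.2 does not make dosing depend on the result. Several of these provisions also refer to a confirmed first seizure, which may come after the interval in question.

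Third, Section 5.1.2 requires medical monitor approval to resume after a related event. That could apply on the IAC reading, because the man stopped. It does not reach a man who never stopped.

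Fourth, with a half-life of about 5.8 days (Section 1.2.2.1) and a visit targeted within 3 days, a 3-day hold leaves 2^(−3/5.8) = 0.70 of the parent drug. A short hold therefore changes exposure only modestly. This limits the importance of the first reading unless the work-up is delayed. It does not touch the second, where dosing could go on without confirmed benefit.

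**Conclusion.** The conflict is real and should be corrected. Section 4.2 either contradicts its own stop instruction or omits the restart condition in the Synopsis and Section 2.2.1, and the text does not show which.

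The documents do not support four stronger inferences that a reader might draw:

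- *That Section 4.2 waives a benefit confirmation required during the work-up.* No passage asks for it then; the drug is simply held. The confirmation applies once the neurologist has determined a first seizure.
- *That Section 4.2 conflicts with the hold after a second seizure.* It fails to repeat the hold, but its note does not permit re-dosing in that case. This is an omission.
- *That about 3.7 men would be harmed.* That figure counts expected first seizures over four months. It assumes the earlier studies' rate and full follow-up of 400 men. How many would be dosed because of this sentence cannot be estimated from the documents.
- *That the seizure estimate is affected.* The primary endpoint counts men with at least one confirmed seizure, and the ambiguity does not change that definition, the sample-size figures or any planned analysis.

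The effect is on patient safety and on consistency across sites, for a small number of men, each with a potentially serious event.

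**What to change.** In Section 4.2, delete the first permissive sentence and insert the rules from the Synopsis and Section 2.2.1:

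1. Any suspected seizure: hold enzalutamide until the neurologist's assessment is complete.
2. Judged not a seizure: enzalutamide may be restarted.
3. Judged a first seizure: restart may precede the IAC assessment, but only after the investigator confirms clinical benefit and if investigator and subject wish it.
4. Second seizure: repeat the hold pending IAC review in the wording those sections already use, with discontinuation if confirmed.

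Make the sentence on dosing during anticonvulsant therapy subject to the condition in item 3.

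No rule is new, and no procedure, visit or data item is added. A man whose event proves not to be a seizure misses doses until he is assessed, but the stop instruction already requires that. The cost is administrative. Because the change affects subject safety, Section 8.3.3 requires IRB/IEC approval before it is implemented, across 25 planned countries (Appendix 12.5) and about 135 centers (Synopsis).
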